5.7.3 Visit Schedule Once Treatment Failure is Reached

1104

When a subject reaches treatment failure prior to the 6 Month visit window, the subject should

1105

be brought back as soon as possible for an unscheduled visit and all 6 Month visit procedures

1106

should be performed. The subject should be directed to remain on medical therapy (if on medical

1107

therapy) until seen for this visit, unless instructed otherwise by the Site Investigator. The subject

1108

should then return for the scheduled 6 Month visit and then the 12 Month visit. After the 12

1109

Month visit, subjects will then continue in the Treatment Failure Identification Phase of the study

1110

with annual visits.

1111 **Chapter 6: Testing Procedures, Questionnaires, Clinical**
1112 **Assessments, and Laboratory Testing**

1113 **6.1 Testing Procedures**

1114 The testing procedures are noted below and details are provided in the Site Procedures Manual.

1115 **6.2 Intraocular Pressure**

1116 Intraocular pressure will be measured using Goldmann tonometry.

1117 **6.3 Refraction and Visual Acuity**

1118 At each protocol visit, a standardized refraction will be performed in both eyes. This will be
1119 followed by testing of visual acuity using ETDRS charts. Both will be administered by a certified
1120 technician masked to treatment group as best as possible.

1121 Although it is not possible to fully mask the technician to whether or not a subject had ONSF, all
1122 subjects will wear hairnets during the testing after randomization through the Week 8 visit in
1123 order to provide masking to VPS.

1124 **6.4 Papilledema Grading**

1125 Site investigators will be trained to grade papilledema using the Frisén scale.⁷⁷

1126 Fundus photography: Digital fundus photographs centered on the optic disc will be taken at each
1127 visit. The severity of papilledema will be graded by the Photography Reading Center (PRC)
1128 using the Frisén scale.^{77,78}

1129 **6.5 Perimetry**

1130 Automated perimetry will be performed using the Humphrey Field Analyzer (HFA) 24-2 full-
1131 threshold program using a size V stimulus in both eyes by a certified technician masked as best
1132 as possible to treatment group. The MOP provides a detailed description of this procedure.

1133 Although it is not possible to fully mask the visual field technician to whether or not a subject
1134 had ONSF, all subjects will wear hairnets during the visual field examination after randomization
1135 through the Week 8 visit in order to provide masking to VPS. The use of a standardized visual
1136 field protocol should limit the influence of the visual field technician on the results of the
1137 examination.

1138 **6.6 OCT**

1139 Spectral-domain OCT evaluations of the optic nerves, peripapillary RNFL, and macula will be
1140 obtained using a Cirrus™ (Carl Zeiss-Meditec, Inc, Dublin, CA) or Spectralis® (Heidelberg
1141 Engineering, Inc, Carlsbad, CA) spectral-domain OCT. The subject must have the same brand of
1142 OCT machine used for data collection at each visit.

1143 **6.7 Lumbar Puncture**

1144 Lumbar puncture is performed as part of usual care at baseline. Although repeat lumbar puncture
 1145 is not considered standard of care, subjects will undergo a second voluntary lumbar puncture for
 1146 CSF opening pressure measurement at the 6-month visit, following the procedure detailed in the
 1147 MOP.

1148 **6.8 Quality of Life Assessment**

1149 The NEI VFQ-25 and the 10-item Neuro-ophthalmic Supplement to the VFQ-25 will be used, as
 1150 well as the SF-36v2.⁷⁹ Testing time is approximately 20 minutes.

1151 **6.9 Headache Disability Rating**

1152 Headache disability will be rated using the HIT-6 (Headache Impact Test),⁸⁰ a 6-item scale that
 1153 is commonly used to rate migraine disability and has been validated for IHH. Testing time is 1-2
 1154 minutes.

1155 **6.10 Neurologic and Physical Examination**

1156 A standard neurological evaluation will be performed at screening. When indicated, a general
 1157 medical examination will be performed.

1158 **6.11 Clinical Laboratory Tests**

1159 CBC with platelet count will be obtained at Baseline and at Weeks 16 and 26 for all subjects.

1160 A comprehensive metabolic profile, including liver function tests, electrolytes, and amylase, will
 1161 be obtained at Baseline and at Weeks 16 and 26 for all subjects.

1162 For subjects taking furosemide, serum potassium and sodium levels will be checked prior to each
 1163 dosage change, after reaching the maximum tolerated dosage, and then at each subsequent visit.

1164 This testing will be performed at a local laboratory.

1165 Routine clinical laboratory tests will be performed locally by the site or the subject's local
 1166 laboratory if travel to the site is not convenient. The Site Investigator will review the laboratory
 1167 values. The Site Investigator will prescribe appropriate supplementation for hypokalemia,
 1168 hyponatremia and symptomatic bicarbonate deficiency, and may enlist the help of the subject's
 1169 primary physician to help manage abnormal laboratory results, if necessary.

1170

Chapter 7: Adverse Event Reporting

1171

7.1 Adverse Events

1172

7.1.1 Definitions

1173 Adverse Event (AE): Any untoward medical occurrence in a study subject, irrespective of the
1174 relationship between the adverse event and the study drug or surgery (see 7.1.2 for what adverse
1175 events require reporting in this protocol).

1176 Serious Adverse Event (SAE): Any untoward medical occurrence that:

- 1177 • Results in death.
- 1178 • Is life-threatening; (a non-life-threatening event which, had it been more severe, might
1179 have become life-threatening, is not necessarily considered a serious adverse event).
- 1180 • Requires inpatient hospitalization or prolongation of existing hospitalization.
- 1181 • Results in persistent or significant disability/incapacity or substantial disruption of the
1182 ability to conduct normal life functions.
- 1183 • Is a congenital anomaly or birth defect.
- 1184 • Is considered a significant medical event by the investigator based on medical judgment
1185 (e.g., may jeopardize the subject or may require medical/surgical intervention to prevent
1186 one of the outcomes listed above).

1187

7.1.2 Reporting Adverse Events

1188 Symptoms and signs, including visual symptoms and headaches, that are considered to be due to
1189 IIIH will be captured on a visit/phone case report form and are not considered to be adverse
1190 events unless SAE criteria are met.

1191 Certain adverse events that are known side effects of acetazolamide and furosemide will be
1192 captured on a visit/phone case report form (including paresthesia, dizziness, nausea, vomiting,
1193 diarrhea, loss of appetite, acid reflux, skin rash, dyspnea, hypercapnia, depression, anxiety,
1194 tinnitus, fatigue) for all subjects, regardless of whether taking study medication. A separate
1195 Adverse Event Form is only completed for these specific events if SAE criteria are met or the
1196 event was severe enough that it resulted in discontinuation of study drug.

1197 Expected symptoms post-surgery will be captured on a visit/phone case report form. A separate
1198 Adverse Event Form is only completed for these specific events if SAE criteria are met or if the
1199 onset date is outside the expected duration of occurrence post-surgery, regardless of intensity.

1200 Laboratory results of interest will be recorded on a laboratory data case report form. A separate
1201 Adverse Event Form is only completed for laboratory abnormalities that are considered clinically
1202 significant by the investigator.

1203 During the first 6 months, all other events (not described above) meeting the definition of
1204 adverse event will be reported on an Adverse Event Form. After the first 6 months, only those
1205 events meeting SAE criteria will be reported on an Adverse Event Form.

1206 **7.1.3 Relationship of Adverse Event to Study**

1207 The study investigator will assess the relationship of any adverse event reported on an Adverse
1208 Event Form to be related or unrelated to a study intervention or procedure by determining if there
1209 is a reasonable possibility that the adverse event may have been caused by the intervention or
1210 procedure.

1211 To ensure consistency of adverse event causality assessments, investigators should apply the
1212 following general guideline when determining whether an adverse event is related:

1213 Yes

1214 There is a plausible temporal relationship between the onset of the adverse event and the study
1215 intervention/procedure, and the adverse event cannot be readily explained by the subject's
1216 clinical state, intercurrent illness, or concomitant therapies; and/or the adverse event follows a
1217 known pattern of response to the study intervention/procedure; and/or the adverse event abates or
1218 resolves upon discontinuation of the study intervention/procedure or dose reduction and, if
1219 applicable, reappears upon re-challenge.

1220 No

1221 Evidence exists that the adverse event has an etiology other than the study
1222 intervention/procedure (e.g., preexisting medical condition, underlying disease, intercurrent
1223 illness, or concomitant medication); and/or the adverse event has no plausible temporal
1224 relationship to study intervention/procedure.

1225 **7.1.4 Intensity of Adverse Events**

1226 The intensity of an adverse event will be rated on a three-point scale: (1) mild, (2) moderate, or
1227 (3) severe. It is emphasized that the term severe is a measure of intensity; thus, a severe adverse
1228 event is not necessarily serious. For example, itching for several days may be rated as severe,
1229 but may not be clinically serious.

- 1230 • MILD: Usually transient, requires no special treatment, and does not interfere with the
1231 subject's daily activities.
- 1232 • MODERATE: Usually causes a low level of inconvenience or concern to the subject and
1233 may interfere with daily activities, but is usually ameliorated by simple therapeutic
1234 measures.
- 1235 • SEVERE: Interrupts a subject's usual daily activities and generally requires systemic
1236 drug therapy or other treatment.

1237 **7.1.5 Coding of Adverse Events**

1238 Adverse events will be coded using the MedDRA dictionary.

1239 **7.1.6 Outcome of Adverse Event**

1240 The outcome of each reportable adverse event will be classified by the investigator as follows:

- 1241 • RECOVERED/RESOLVED: The subject recovered from the AE/SAE without sequelae.
1242 Record the AE/SAE stop date.
- 1243 • RECOVERED/RESOLVED WITH SEQUELAE: The event persisted and had stabilized
1244 without change in the event anticipated. Record the AE/SAE stop date.
- 1245 • NOT RECOVERED/NOT RESOLVED: An ongoing AE/SAE is defined as the event
1246 was ongoing with an undetermined outcome.
- 1247 ◆ An ongoing outcome will require follow-up by the site in order to determine the final
1248 outcome of the AE/SAE.
- 1249 ◆ The outcome of an ongoing event at the time of death that was not the cause of death,
1250 will be updated and recorded as “resolved” with the date of death recorded as the stop
1251 date.
- 1252 • FATAL: A fatal outcome is defined as the SAE that resulted in death. Only the event
1253 that was the cause of death should be reported as fatal. AEs/SAEs that were ongoing at
1254 the time of death; however, were not the cause of death, will be recorded as “resolved” at
1255 the time of death.
- 1256 • UNKNOWN: An unknown outcome is defined as an inability to access the subject or the
1257 subject’s records to determine the outcome (for example, a subject that was lost to
1258 follow-up).

1259 All clinically significant abnormalities of clinical laboratory measurements or adverse events
1260 occurring during the study and continuing at study termination should be followed by the
1261 subject’s physician and evaluated with additional tests (if necessary) until diagnosis of the
1262 underlying cause, or resolution. Follow-up information should be recorded on source
1263 documents.

1264 If any reported adverse events are present when a subject completes the study, or if a subject is
1265 withdrawn from the study due to an adverse event, the subject will be contacted for re-evaluation
1266 within 2 weeks. If the adverse event has not resolved, additional follow-up will be performed as
1267 appropriate. Every effort should be made by the Investigator or delegate to contact the subject
1268 until the adverse event has resolved or stabilized.

1269 **7.2 Pregnancy Reporting**

1270 If pregnancy occurs during the 6-month RCT, study drug will be discontinued. The occurrence of
1271 pregnancy will be reported on an AE Form.

1272 **7.3 Timing of Event Reporting**

1273 Serious, unexpected treatment-related adverse events must be reported to the Coordinating
1274 Center within 24 hours via completion of the online serious adverse event form.

1275 Other reportable adverse events as defined in section 7.1.2 will be reported within 3 days of the
1276 investigator becoming aware of the event by completion of an electronic case report form.

1277 The Coordinating Center will notify all participating investigators of any adverse event that is
1278 serious, related, and unexpected. Notification will be made within 10 working days after the
1279 Coordinating Center becomes aware of the event.

1280 Each principal investigator is responsible for reporting serious study-related adverse events and
1281 abiding by any other reporting requirements specific to his/her Institutional Review Board or
1282 Ethics Committee.

1283 The sponsor will report any serious, unexpected treatment-related adverse events to the FDA.

1284

1285 **7.4 Stopping Criteria**

1286 **7.4.1 Subject Discontinuation of Study Drug**

1287 Rules for discontinuing study drug use are described below.

- 1288 • The investigator believes it is unsafe for the subject to continue to receive the drug. This
1289 could be due to the development of a potential side effect of the drug, a new medical
1290 condition or worsening of an existing condition; or subject behavior contrary to the
1291 indications for use of the drug that imposes on the subject's safety
- 1292 • The subject requests that the treatment be stopped
- 1293 • Subject pregnancy during 6-month RCT (discontinuation at investigator discretion during
1294 Treatment Failure Identification Phase)

1295 Even if the study drug is discontinued, the subject will be encouraged to remain in the study
1296 through the final study visit.

1297 **7.5 Medical Monitor**

1298 A Medical Monitor will review all reported adverse events reported on an Adverse Event Form,
1299 solicited events captured on a visit/phone case report form, and laboratory abnormalities.

1300 The Medical Monitor will assess each event for appropriate coding of intensity, criteria for SAE,
1301 relationship to study drug/procedure, and MedDRA classification. The Medical Monitor's
1302 coding will be considered final.

1303 **7.6 Independent Safety Oversight**

1304 A Data and Safety Monitoring Committee (DSMC), selected by the National Eye Institute, will
1305 provide study oversight. The Committee will be sent serious, unexpected, treatment-related
1306 adverse events for expedited review and all adverse events in a cumulative report approximately
1307 every 6 months.

1308 **7.7 Criteria for Suspending or Terminating Overall Study**

1309 There are no pre-specified criteria for suspending or terminating the study. Such decisions will
1310 be made by the DSMC based on their review of accumulated safety data.

1311

Chapter 8: Miscellaneous Considerations

1312

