416 Assessment for and implementation of adjustment for baseline covariates will follow methods
417 described in *Section 3.2.3*.

419 **3.3.4 Investigation of Treatment by Covariate Interactions**

420 Investigation of interaction between treatment group and selected baseline covariates will follow
421 methods described in *Section 3.2.4*.

422

423 **3.3.5 Verification of Model Assumptions**

424 Methods described in *Section 3.2.5* will be used to check underlying assumptions of the
425 statistical model for each outcome.

426

427 **3.3.6 Treatment of Missing Data**

428 Methods described in *Section 3.2.6* will be used to impute missing data at Month 6 for
429 continuous outcomes.

430

431 Missing values of Month 6 visual field examination status will not be imputed.

432

433 **3.4 Compliance Outcomes**

434 Data concerning compliance with acetazolamide (pill counts, serum bicarbonate levels) and
435 surgical therapy will be summarized by treatment group and visit. Subjects with two eligible
436 eyes will have this information summarized by eye as well as by treatment group and visit.

437

438 **3.5 Analysis of Safety and Tolerability Outcomes**

439 **3.5.1 Adverse Events**

440 All reportable adverse events will be tabulated by treatment group in a listing of each reported
441 Medical Dictionary for Regulatory Activities (MedDRA) term and summarized over each
442 MedDRA System Organ Class. Details will be provided in a listing of each event.

443 In addition, the following will be tabulated by treatment group. When applicable, events will be
444 tabulated by eye within person:

- 445 • Number of adverse events per subject
- 446 • Number of subjects with at least one event
- 447 • Number of subjects with at least one event per person-month (person-month based on
448 subject duration in the study)
- 449 • Number of serious adverse events per subject
- 450 • Number of subjects with at least one serious adverse event
- 451 • Number of hospitalizations and reasons for the hospitalization (overall and per subject,
452 separately)
- 453 • Number of adverse events thought by investigator to be related to study drug and
454 frequency of each type of such event
- 455 • Number of subjects who stopped the intervention in response to an adverse event

456 For binary variables (occurrence of at least one event, occurrence of at least one serious adverse
457 event, occurrence of at least one hospitalization, occurrence of at least one adverse event related

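### A non-serious post-surgical symptom that starts within its expected period and outlasts it never triggers an Adverse Event Form, so persistent non-serious harm in operated subjects can be understated

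*Protocol*

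**What the plan says.** Protocol 7.1.1 defines adverse events broadly ("Adverse Event (AE): Any untoward medical occurrence in a study subject, irrespective of the" relationship to study drug or surgery) and leaves it to 7.1.2 to say which of them must be reported.

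For surgery, 7.1.2 sets the default: "Expected symptoms post-surgery will be captured on a visit/phone case report form". The exception follows: a separate "Adverse Event Form is only completed for these specific events if SAE criteria are met or if the" "onset date is outside the expected duration of occurrence post-surgery, regardless of intensity".

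The same section has a parallel rule for a list of known acetazolamide and furosemide side effects, applied to all subjects whether or not they take the drug. These go on an Adverse Event Form only if SAE criteria are met or the "event was severe enough that it resulted in discontinuation of study drug". Any other adverse event in the first 6 months goes on the form. After 6 months only SAEs do, in every arm.

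SAP 3.5.1 then states: "All reportable adverse events will be tabulated by treatment group in a listing of each reported" MedDRA term. It goes on to compare the arms with Fisher exact tests and count models.

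**The concern.** What separates ordinary recovery from lasting harm is whether a symptom goes away. The surgical rule never asks this. It compares a start date with a duration, so a mild symptom that begins just after the expected period must be reported, while one that begins on the first day and is still present months later need not be.

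The trial compares two operations plus medical therapy with medical therapy alone. Persistent symptoms after an operation, even non-serious ones, belong in that risk-benefit comparison. If the reporting rule filters them out before analysis, the adverse-event tables cannot show them, however well the SAP is carried out.

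**Working it through.** No plan figure is attached to this rule, so there is nothing to reproduce. The check is to run the possible cases through 7.1.2 and follow the one that escapes.

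**Step 1. Cases for an expected post-surgical symptom in the first 6 months**

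| Case | SAE trigger | Onset trigger | Adverse Event Form |
|---|---|---|---|
| (a) Starts in the period, resolves in it, non-serious | No | No | No |
| (b) Starts in the period, outlasts it, non-serious | No | No | **No** |
| (c) Starts in the period, outlasts it, meets an SAE criterion | Yes | No | Yes |
| (d) Starts after the period, any intensity | Not needed | Yes | Yes |

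The rule cannot tell (a) from (b). That is the gap.

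**Step 2. What happens to case (b) afterwards**

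- Protocol 7.3 treats 7.1.2 as the definition of a reportable event.
- Protocol 7.1.3 has the investigator judge relatedness for events on an Adverse Event Form. Case (b) has none.
- Protocol 7.1.6 assigns an outcome, including not resolved, to reportable events, and its re-contact within 2 weeks of completion applies to reported events. Case (b) receives neither.
- SAP 3.5.1 tabulates reportable events. On the natural reading, case (b) is outside those tables and the comparisons built on them.

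**Step 3. Who is affected**

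The rule applies only after an operation. In the first 6 months the same symptom in an unoperated subject would fall under the default rule and go on a form, unless another exemption covers it. Before crossover the gap therefore sits essentially in the ONSF and VPS arms. Under Protocol 5.7.2, treatment after failure preferably comes from another arm, so medical-arm subjects who are then operated on come under the rule too.

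**Step 4. Comparison with the drug side-effect rule**

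That rule covers all three arms. It also has no persistence trigger: a chronic side effect in a subject who stays on drug gets no form. Its second trigger is drug discontinuation, whereas the surgical rule's is late onset.

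**Step 5. Size**

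Neither document lists the expected symptoms, their expected durations or any rate. The manual of procedures may give the first two, but that would not change an onset-only trigger. No effect on event counts can be calculated.

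**The case against.** The strongest reply is that little of importance is lost. Lasting harm is often SAE territory: 7.1.1 includes an event that "Results in persistent or significant disability/incapacity or substantial disruption of the" ability to live normally, and one that "Is considered a significant medical event by the investigator based on medical judgment". The symptom is still an adverse event by definition and is still recorded. Under Protocol 7.5 the Medical Monitor reviews solicited events on the visit/phone form and assesses intensity, seriousness and relationship. Procedure complications are a named safety measure in Protocol 1.4.2. SAP 3.8 tabulates surgical complications, reoperations, shunt revisions and headache by visit, and the DSMC weighs surgical complications.

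Most of this stands, and it limits the point to persistent, non-serious symptoms. It does not close the gap. Protocol 7.1.4 itself says that a severe event need not be serious, so the SAE route will not catch everything that matters. Neither document specifies a between-arm comparison of post-surgical symptoms held only on the case report form, or of how long they last. The surgical-complications table is listed separately for the two surgical groups, without saying whether it includes expected symptoms or measures persistence.

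Three stronger readings are tempting, and the documents do not support them:

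- *Late onset is the only route to a form, or the symptom goes unrecorded.* The SAE trigger is in the same sentence, and the case report form captures the symptom.
- *The protocol tells sites to ignore severity.* The words on intensity widen the late-onset trigger, so that even a mild late symptom is reported. It remains true that intensity alone triggers nothing for a symptom that starts on time.
- *The rule biases the trial in favour of surgery.* The drug rule also drops persistent events, in all arms. Protocol 4.1.4 tapers acetazolamide from the day of surgery in the VPS arm, so those omissions may weigh more on medical therapy. The net direction is not determined.

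**Conclusion.** The concern holds for non-serious expected post-surgical symptoms. For these, the onset date is the only trigger, and a symptom that starts on time and persists is left off the Adverse Event Form and, on the natural reading, out of the SAP 3.5.1 comparisons. This can understate persistent non-serious harm in operated subjects. It is a consequence of a stated rule, not a missing detail.

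The conclusion rests on two readings: that reportable in the SAP means reportable under Protocol 7.1.2, and that sites apply the sentence as written.

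The size is unknown. A reader might illustrate it by assuming that 5–15% of the 120 subjects assigned to surgery (2 × 60) have such a symptom. That gives 0.05 × 120 = 6 to 0.15 × 120 = 18 subjects without a form. Likewise, a constructed 6/60 against 0/60 (Fisher exact p = 0.027) would be reported as 0/60 against 0/60. Nothing in the documents anchors either assumption, so these figures show how the rule works and are not evidence of impact.

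**What to change.** In Protocol 7.1.2, keep the SAE trigger and replace the onset test with one that also covers persistence, for example: *a separate form is completed if SAE criteria are met, or if the symptom starts in, or persists into, the time after the expected post-surgical duration, whatever its intensity.* Carry the same wording into the case report form instructions.

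Do not add a trigger for symptoms rated severe. It does not follow from the persistence gap. It would also make ordinary early postoperative symptoms reportable while severe drug side effects without discontinuation stay exempt, which creates a new imbalance.

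Where forms already completed cannot support the new trigger, pre-specify in the SAP a by-arm table of expected post-surgical symptoms captured on the visit/phone form and still present after the expected duration. State there where the expected durations are defined.

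The cost is one sentence in the protocol, some additional Adverse Event Forms, and one SAP table if the fallback is needed. Both routes need stop dates, or presence recorded visit by visit, on the case report form, and the documents do not say whether these are collected. The change concerns reporting only. Unless the SAE-only rule after 6 months is also changed, it acts within the first 6 months.
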